6.4. Sample Size and Power

Sample size was calculated based on the sample required for our upcoming randomized placebo-controlled crossover studies of anakinra for mitigating features of allergen-induced asthma exacerbation. We hypothesize that anakinra treatment reduces the LPR, as assessed by the change in maximum percentage fall in %FEV1 during hours 3-10 following allergen challenge. We have developed protocols for two anakinra treatment clinical trials, each of which will incorporate a crossover study design: one will provide anakinra treatment (v. placebo) immediately after the EPR, and one will provide anakinra treatment (v. placebo) at the onset of the LPR (i.e. 3 hours after the EPR).

We calculated the sample size for the anakinra treatment protocols using a model of inhaled allergen challenge similar to what we propose in this project (69) based on a paired t test. The maximal drop in %FEV1 during the LPR was $25.6\% \pm 9.8\%$ (SD). To detect a 50% attenuation of the drop in %FEV1 during the LPR (12.8%) by anakinra v. placebo treatment, assuming that group-wise standard deviations are similar (10.28% for anakinra; 9.8% for placebo), with $\beta=0.9$ & $\alpha=0.05$, a sample size of 6.4 would be required for each anakinra protocol. We estimate that 25% of subjects will require rescue short-acting beta agonist treatment during the EPR or the LPR, and will additionally account for a 25% dropout rate for a crossover study, inflating our required sample size to at least **N=12** for each anakinra treatment protocol.

Previous studies of inhaled allergen challenge models in allergic asthmatics have found that 50-70% of subjects who undergo challenge will experience an EPR^{19,20}. House dust mite is one of the most commonly utilized allergens for inhaled challenge. Gauvreau et al²¹ reported that >75% of house dust mite allergen challenged volunteers who display an EPR will also have a LPR. Due to the lack of data on the frequency of LPR with cat hair allergen inhalation challenge and given that both are perennial allergens, we will extrapolate the results from house dust mite challenge to estimate the number of participants needed to screen. Using a conservative estimate of 50% of our screened volunteers with a EPR and 50% of those with a LPR, we will screen up to 100 subjects to identify at least **25** LPR subjects eligible to enroll into the anakinra treatment studies. Screening will stop following identification of 25 LPR subjects.

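### Does the 6.4 subjects per anakinra trial in Section 6.4 understate what the named paired t test needs?

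*Combined protocol and SAP*

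**What the plan says.** Section 6.4 takes this study's size from trials that come after it: "Sample size was calculated based on the sample required for our upcoming randomized placebo-controlled crossover studies of anakinra". The stated hypothesis is directional: "We hypothesize that anakinra treatment reduces the LPR". The method is given as a model "similar to what we propose in this project (69) based on a paired t test".

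The inputs are a late-phase fall in %FEV1 of 25.6 with SD 9.8, a halving of that fall (12.8), alpha 0.05, and 90% power printed as beta=0.9. The spreads are entered "assuming that group-wise standard deviations are similar (10.28% for anakinra; 9.8% for placebo"). The result is "a sample size of 6.4 would be required for each anakinra protocol".

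Two allowances are then applied. The first is for rescue: "We estimate that 25% of subjects will require rescue short-acting beta agonist treatment during the EPR or the LPR". The second is for dropout: the plan "will additionally account for a 25% dropout rate for a crossover study". Together they bring the number to at least 12 per trial. Two trials of 12 make 24, and the section ends the search just above that: "Screening will stop following identification of 25 LPR subjects". Section 6.3 adds that, because the sample size allows for extra individuals, missing data should not much affect power.

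**The concern.** A paired t test depends on the SD of the within-subject differences. Section 6.4 gives two group-wise SDs instead, with no correlation to link them, and does not say whether the test is one- or two-sided. Section 6.3 gives only a 0.05 criterion. The source of the inputs is cited as number 69, while the reference list in Section 14 ends at 22, so the missing values cannot be traced from these documents.

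Entering a printed SD directly into the t test does not return 6.4. A two-sided normal approximation at an SD of about 10 does. That suggests the small-sample correction was left out, and it matters most at around six pairs.

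If 9 pairs were truly needed, the plan's own two allowances would give 9/(0.75 × 0.75) = 16 per trial, not 12. Two trials with separate subjects would then need 32 responders, while screening stops at 25.

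**Working it through.** **Inputs (Section 6.4).** Difference d = 12.8; group-wise SDs 10.28 and 9.8; alpha 0.05; power 0.90. The correlation r and the sidedness are not printed, so both are varied below.

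**Reproducing 6.4.** The normal approximation is n = (SD × (z_alpha + 1.282)/12.8)², with z_alpha = 1.960 two-sided or 1.645 one-sided.

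- SD 9.8: 6.16 two-sided, 5.02 one-sided
- SD 10.0: 6.41 two-sided, 5.23 one-sided
- SD 10.28: 6.78 two-sided, 5.52 one-sided

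The printed 6.4 matches the two-sided approximation at an SD of about 10. This is its likely origin, but the documents do not prove it.

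**The named test with a printed SD as the SD of differences.** Power comes from the noncentral t with n − 1 degrees of freedom and noncentrality 12.8 × √n / SD. The pairs needed for 90% power are:

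- SD 9.8: 8.31 two-sided, 6.63 one-sided
- SD 10.0: 8.56 two-sided, 6.83 one-sided
- SD 10.28: 8.92 two-sided, 7.11 one-sided

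In whole pairs that is 9 two-sided, and 7 (7 to 8 across the range) one-sided.

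**What that substitution assumes.** SD of differences = √(10.28² + 9.8² − 2 × r × 10.28 × 9.8) = √(201.72 − 201.49r). At r = 0.5 this is 10.05. Using a group-wise SD of about 10 is therefore the same as assuming r of about 0.5.

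**Where the t test itself returns 6.4.** Two-sided, at an SD of differences of 8.08 (r = 0.68). One-sided, at 9.56 (r = 0.55).

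**Pairs left out of 12.** The plan's inflation is 6.4/0.75/0.75 = 11.4, rounded up to 12. If both losses remove the pair, 12 × 0.75 × 0.75 = 6.75 remain, so 6 to 7. If only dropout removes it, 12 × 0.75 = 9 remain.

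**Power over assumed correlations (two-sided / one-sided, %).**

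| r (assumed) | SD of differences | Whole pairs for 90% | 6 pairs | 7 pairs | 9 pairs |
|---|---|---|---|---|---|
| 0.3 | 11.89 | 12 / 9 | 57 / 73 | 66 / 81 | 81 / 90 |
| 0.4 | 11.01 | 10 / 8 | 63 / 79 | 73 / 86 | 86 / 94 |
| 0.5 | 10.05 | 9 / 7 | 71 / 85 | 80 / 91 | 92 / 97 |
| 0.6 | 8.99 | 8 / 6 | 79 / 91 | 88 / 95 | 96 / 99 |
| 0.7 | 7.79 | 7 / 5 | 89 / 96 | 95 / 98 | 99 / 99.8 |

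With all 12 pairs and an SD of 10, power is 98% two-sided and 99% one-sided.

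The conclusion turns on three unprinted facts: the correlation, the sidedness, and whether a rescued subject's pair leaves the analysis. Power of 71 to 80% needs a two-sided test, r of about 0.5 and the loss of every rescued pair, all at once. Two-sided at r = 0.5, keeping the rescued pairs gives 92%.

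**The case for a change.** The strongest case for a change is that a stated 90% power ought to be reproducible with the stated test, and this one is not. The likely route to 6.4 is an approximation that is poor at this size. The two 25% allowances add no margin beyond 6.4; they only restore it, leaving 6.75 pairs. At a correlation of 0.3, two-sided power would be 57 to 66%. The target of 25 responders does rest on this figure, since it covers two trials of 12, and Section 6.3 leans on the same calculation. Printing the inputs would cost only a few words.

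Much of this stands. The inputs are absent, the citation cannot be followed, and beta=0.9 is loose notation for power of 0.9. What does not stand is the step from an unprinted input to a wrong number. The SDs are labelled as group-wise, and the plan does not say that either one is the SD of differences. On a one-sided reading, which the directional hypothesis permits but does not establish, the need at an SD of about 10 is 7 whole pairs, and 6.4 also rounds up to 7. A rescue rate listed as an inflation factor does not say that rescued subjects are dropped from the analysis. The 12 is printed as a minimum.

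**Conclusion.** The concern does not call for a change. The calculation is under-described, but the documents do not show that 6.4, or the 12 built on it, is wrong. With r of about 0.5, a two-sided test and every rescued pair lost, 12 subjects would give 71 to 80% power. With r of about 0.7, or with rescued pairs kept at r = 0.5, the same 12 give roughly 90% or more two-sided (89 to 95% and 92%). Nothing in these documents selects among these cases.

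The missing inputs concern the power of the anakinra trials. Their separate protocols have been developed but are not in these documents, and that is where an analyst would settle the correlation, the sidedness and the handling of rescued pairs. This study's primary endpoint is the identification of subjects with a late-phase fall of at least 15%, which has no hypothesis test to power. The ceiling of 100 screened comes from the responder target and the two 50% response assumptions (100 × 0.5 × 0.5 = 25). Writing the inputs into Section 6.4 would alter no participant, endpoint or analysis here. The citation number and the beta notation are clerical slips. This conclusion would change only if the later protocols showed a low correlation together with a two-sided test and exclusion of rescued pairs.

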6.5. Interim Analysis

There are no planned interim analyses.

7 STUDY INTERVENTION

- **Description:** Standardized cat hair (*Felis catus*) allergenic extract, 10,000 BAU/mL
- **Receipt/Storage:** Product will be shipped from the manufacturer (Stallergenes Greer, [name]) to the UNC Investigational Drug Pharmacy.
- **Packaging/labeling:** The UNC Investigational Drug Service (IDS) will prepare allergen dilutions, and each dose vial will be labeled with the dilution (for example: 39 BAU/mL).
- **Dosing:** The University of North Carolina Investigational Drug Pharmacy (IDS) will use commercial vials of preservative-free, sterile 0.9% sodium chloride for injection manufactured by Abbott or Hospira. Prepared dilutions will be stored in the University of North Carolina Investigational Drug Pharmacy refrigerator which is temperature controlled and which will alarm if the refrigerator exceeds a specified range. Doses will be made up no more than 24 hours prior to administration. Doses of allergen will include concentrations of zero (diluent), 0.31, 0.61, 1.22, 2.44, 4.89, 9.77, 19.5, 39, 78.13, 156.25, 312.5, and 625 BAU/mL. Prior to study initiation, the IDS will create a formulation sheet with detailed instructions for the serial dilutions for the investigational agent used in this protocol. An information sheet will also be created, and trained staff members will be in-serviced regarding the preparation of study drug. The dilutions are prepared in a laminar air flow hood by a pharmacy technician. Each step of the dilution process is checked by a pharmacist, and dose vials are labeled as each dilution is complete.
- **Treatment compliance and adherence:** Given the nature of this protocol, all doses of study product will be administered directly by study personnel.
- **Drug return/destruction:** Unused dilutions of allergen will be discarded at the end of the allergen challenge procedure.
- **Drug Accountability:** Drug storage, handling and dispensing will be the responsibility of the IDS. Documentation of administration and destruction of unused product will be the responsibility of the study personnel.

8 STUDY INTERVENTION ADMINISTRATION

As this is an open-label single arm intervention study, all participants will receive the same treatment without blinding.

9 SAFETY MANAGEMENT

9.1. Definition of Adverse Event (AE) and Serious Adverse Event (SAE):

Adverse events will be recorded and reported according to 21 CFR 312.32. An adverse event for a given volunteer will be defined as any untoward medical occurrence associated with use of the investigational agent whether or not considered related and will also include failure of any of the safety criteria outlined above. Additionally, minor upper respiratory tract infections occurring within 10 days of the exposure will be considered adverse events. Other, non-specified clinical illnesses, which occur within 10 days of each challenge will also be reported as an AE. Specific potential adverse events which may occur with allergen challenge include the following: Allergic Reaction, Cough, Dyspnea, Urticaria, Syncope, and Voice Changes.

Also, any decrease in lung function or increase in symptom score, as outlined in section 4.8. will be considered an adverse event. Failure of a total symptom score to return to no greater than 6 above baseline within 10 days will be considered an adverse event. Any symptoms that induce a volunteer to seek medical attention from any provider within 10 days of challenge will be considered an adverse event.

9.2. Grading Criteria

Adverse events will be graded using Common Terminology Criteria for Adverse Events v3.0, (CTCAE website at <http://ctep.cancer.gov/reporting/ctcnew.html> and <http://safetyprofiler-ctep.nci.nih.gov/CTC/CTC.aspx>). Symptom scores will be graded as outlined elsewhere in this application.

The severity grades of AE's are defined as follows:

Grade 1: Mild AE

Grade 2: Moderate AE

Grade 3: Severe AE

A serious adverse event will be defined as any event that requires hospitalization or results in, life threatening illness or injury, permanent (or likely to be permanent) illness or injury (CTCAE Grade 4), or death, (CTCAE Grade 5), if these events occur within 10 days of challenge (or if the clinical scenario leading up to hospitalization, illness, injury or death begins within 10 days of a challenge).

9.3. Risks to Subjects

At the doses proposed in this study, the most significant predictable risk to subjects as a result of allergen inhalation is development of immediate airway obstruction (bronchospasm) during the EPR, which would cause shortness of breath, cough and/or wheeze. This drop in FEV₁ should be short lived (maximal 10 to 30 minutes after allergen) and reversible with medications such as beta agonists (albuterol). This effect is similar to the effect of methacholine, which is an FDA-approved agent employed for the diagnosis of airway reactivity and asthma.

Other possible risks include development of a LPR to allergen inhalation. This occurs in approximately 50% of asthmatics challenged, consisting of similar symptoms described for the EPR. Since an important secondary endpoint of this study is to identify which subjects have a late asthmatic response, albuterol for rescue prior to the 10 hour post challenge time point will only be employed if the FEV₁ does not show spontaneous improvement, and/or if the subject has distress and requests rescue. All subjects will be given 4 puffs of albuterol 10 hours post-challenge with additional doses given based on FEV₁ and subject distress.

Sputum induction may induce cough, chest tightness or bronchospasm, and albuterol will be immediately available.

Venipuncture carries a risk of hematoma, and this procedure will be performed only by trained staff members.

There is no risk to measurement of eNO since subjects are simply asked to exhale into a mouthpiece.

Nasal ELF collection is associated with a rare risk of sneezing.

There is no known risk associated with HRV monitors or ASSIST devices. The ASSIST devices are under development and are not in clinical use, therefore no data collected from them will impact subject management

or care in this study. Heart rate, respiratory rate, blood pressure, and oxygen saturation will be monitored during the visits using standardized equipment approved for clinical use.

There is a potential risk for breach of confidentiality and privacy.

9.4. Measures to Minimize Risk

Only clinically healthy volunteers will be recruited for this project. Further, subjects will be deferred for challenge until 4 weeks after complete resolution of each of the following acute illnesses: viral respiratory tract infection, pneumonia or bronchitis requiring antibiotic therapy (must be off antibiotics and well for 4 weeks after the last dose of antibiotics), or acute illness resulting in fever. Also, unspecified illnesses, which in the judgment of the investigator increase the risks associated with allergen inhalation challenge, will be a basis for exclusion.

All subjects will need to fulfill objective lung function and symptom criteria prior to initiating the challenge study. Subjects not meeting these criteria on the morning of the challenge will not proceed with the allergen challenge:

1. FEV₁ of at least 80% of predicted and a ratio of FEV₁ to Forced Vital Capacity (FVC) of at least .70 (without use of bronchodilating medications for 8 hours, anticholinergic therapy (such as ipratropium) within 2 hours, or antihistamines within 5 days prior to challenge).
2. Baseline oxygen saturation of at least 95%.
3. No history of asthma exacerbation requiring systemic corticosteroid treatment, visit to an emergency room or hospitalization within 12 months of inhalation challenge.
4. No current history of requiring short-acting beta agonists more frequently than every 8 hours for asthma symptoms. Any use of albuterol in the week prior to allergen challenge will be reviewed by the study physician.
5. No history of viral respiratory tract symptoms within 4 weeks of challenge.

Female subjects of child-bearing potential will undergo urine HCG testing for pregnancy within 48 hours prior to administration of any challenge.

A physician familiar with the protocol will be available for all challenge procedures. Emergency treatment with albuterol (via MDI or nebulizer), oxygen, oral corticosteroids, oral cetirizine, and epinephrine (subcutaneously or intramuscularly) will be available to those subjects who require such therapy. An emergency “crash cart” with standard emergency medications, IV fluids and a defibrillator are is also readily available in the UNC CTRC as well as at CEMALB in the unlikely event of a medical emergency during any challenge or study visit.

If the covering physician feels that the subject’s respiratory status is such that providing an induced sputum sample or performing methacholine challenge would place them at increased risk for significant bronchospasm, we will prioritize spirometry assessments (as part of routine clinical care) and not obtain induced sputum samples or perform methacholine challenge for that subject.

All subjects will be monitored in the CTRC for 10 hours following allergen challenge as outlined in previous sections. Upon discharge to either the subject's home or local hotel, subjects will be provided with an albuterol inhaler with aerochamber and a single dose of oral prednisone 60 mg, clear instructions for use of these medications in the event of bronchoconstriction, and the contact information for the on-call physician. In the event of post-challenge bronchoconstriction that does not improve with albuterol, subject will be instructed to present to the UNC emergency department for further evaluation and management.

Subjects will also be assessed the morning after the allergen challenge in the CEMALB. If the subject has wheezing on physical examination the morning after the inhaled allergen and/or has an FEV₁ that is decreased $\geq 15\%$ from baseline measures (indicating that they are still experiencing a late phase response), they will be given a single dose of prednisone 60 mg and continue following instructions from the provided asthma action plan for albuterol use. These subjects will be contacted by phone within 24 hours of receiving the dose to assess asthma symptoms and will be evaluated in person within 48-72 hours of the dose to monitor FEV₁ and to assess the need for continued therapy.

In addition, all subjects will receive a follow-up call 48 hours after challenge (24 hours after the follow-up sputum induction) to ensure that subjects are well, and all subjects will be provided with a contact telephone number for access to a study physician who is on call 24 hours/day. If it is discovered during the 48 hour follow up phone call that the subject has continued to require albuterol for 48 hours after the inhaled allergen challenge, they will be given a single dose of prednisone 60 mg and continue following instructions from the provided asthma action plan for albuterol use. These subjects will be contacted by phone within 24 hours of receiving the dose to assess asthma symptoms and will be evaluated in person within 48-72 hours of the dose to monitor FEV₁ and to assess the need for continued therapy.

Subjects who are withdrawn for medical concerns related to the study, such as but not limited to prolonged decreased FEV₁ or persistent wheezing, will be followed by study physicians until resolution of these events. As this is a screening protocol, these subjects will not be replaced.

Multiple actions will be taken to minimize the risk of breach of privacy or confidentiality, including conducting study visits in private clinic rooms, keeping all paper case report forms in a locked office in a secured building, using study identification numbers instead of personal identifiers whenever possible, etc. Please see section 10.2. for a detailed description of these procedures.

9.5. Reporting of AEs and SAEs

UNC-Chapel Hill Human Research Protection Program Standard Operating Procedures will be followed for reporting adverse events/unanticipated problems to the Biomedical IRB and NC TraCS DSMB. All SAEs will be reported to the CBER of the FDA as well as to the UNC OHRE, DSMB, and the NIH sponsor within 24 hours of recognition of the event, including the filing of an IND safety report. Adverse events will be reported to both the FDA, UNC IRB, and DSMB on no less than a quarterly basis, or when the protocol is completed. If criteria for suspension of the protocol are met, then the FDA and UNC IRB will be notified within 24 hours.

All subjects with a non-fatal SAE will be evaluated medically by a study physician, in concert with their own physician as appropriate. Likewise, all subjects with an adverse event will be examined and evaluated by a study physician. All assessments will include the same lung function and vital sign assessments outlined for challenge observation. Other assessments will be undertaken as needed. Any unspecified event, which in the judgment of the PI of the study, constitutes an unusual, unexpected or prolonged event (greater than 96 hours) will be reported to both the FDA, the UNC IRB, and the NC TraCS DSMB.

Failure to meet the following safety criteria would result in suspension of the study pending discussion with the DSMB and UNC IRB.

1. No occurrence of any Serious Adverse Event
2. Each SAE and the events listed in 2 a-g would be reported to the FDA, IRB, and DSMB and discussed before performing subsequent challenges or enrolling further participants. In addition, no more than 20% of subjects will fail the individual safety criteria outlined below. As it is anticipated that 100 subjects will be recruited for this screening protocol, then 20 or more subjects who fail individual safety measures will result in suspension of further study until consultation with the CBER of the FDA. Additionally, in order to further monitor safety, we will assess this after completion of 20 subjects, and annually.
 - a. Less than or equal to 40% decrease in FEV₁ or FVC from pre-challenge values following EPR or the LPR to cat hair allergen (the target endpoint is a $\geq 20\%$ decrease in FEV₁ from baseline during the EPR and a $\geq 15\%$ decrease in FEV₁ from baseline during the LPR).
 - b. If albuterol is employed as rescue, FEV₁ must recover to within 90% of baseline value within 20 minutes.
 - c. Oxygen saturation should remain $\geq 93\%$ throughout the challenge period and must be no lower than 2% of baseline measure.
 - d. Albuterol for rescue therapy should be required no more than three times within the first hour after challenge
 - e. Albuterol for rescue therapy should be required no more than three times within 12 hours of discharge.
 - f. FEV₁ should return to within 90% of baseline value at the study discontinuation visit which occurs within 10 days after allergen challenge.
 - g. No occurrence of an asthma exacerbation associated with inhalation challenge requiring more than a single dose of prednisone (60 mg).

A Data Safety Monitoring Board (DSMB) through the NC TraCS Institute will independently review all research activities outlined for the study protocol.

To ensure correct reporting, with each subject binder (in the Case Report Form), we have added a discharge worksheet to capture the above information to ensure availability in real time and to guarantee that we do not overlook a violation of safety criteria.

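### Section 9.5 states the aggregate safety suspension rule both as a percentage and as a fixed count; the two conflict at 20 of 100 and diverge if fewer than 100 subjects are challenged

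*Combined protocol and SAP*

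**What the plan says.** Section 9.5 lists individual safety criteria (items a to g: size of fall in FEV₁ or FVC, recovery after albuterol, oxygen saturation, rescue use, FEV₁ at discontinuation, prednisone use). It then sets a limit on how many subjects may fail them, in two forms:

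- As a proportion: "no more than 20% of subjects will fail the individual safety criteria outlined below".
- As a count, converted on the expectation of a 100-subject study: "then 20 or more subjects who fail individual safety measures will result in suspension of further study". The suspension lasts until the FDA's CBER has been consulted.

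On timing it says "in order to further monitor safety, we will assess this after completion of 20 subjects, and annually", with no threshold or denominator for those looks.

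Two other safeguards stand beside this rule. Any serious adverse event suspends the study. Each such event, and each failure of items a to g, is to be reported and "discussed before performing subsequent challenges or enrolling further participants". Section 9.6 adds DSMB review after the first 6 subjects and every 6 months, without a failure-rate threshold.

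On study size, section 6.4 says "we will screen up to 100 subjects to identify at least" 25 late phase response (LPR) subjects, and "Screening will stop following identification of 25 LPR subjects". So 100 is a ceiling.

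**The concern.** The two forms are presented as one rule but are equivalent at no sample size that the section names. At 100 they differ by one subject. Below 100 they separate, because the count stays at 20 while 20% of the subjects shrinks. At the first scheduled look, after 20 subjects, the count could be met only if every subject had failed.

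At stake is when accumulated failures oblige the study to stop and consult CBER. Apart from the serious adverse event criterion, this is the only study-level numerical trigger in section 9.5. Two people applying it in good faith to the same data could reach opposite decisions.

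**Working it through.** **1. The plan's own figures.** 0.20 × 100 = 20, which reproduces the count in section 9.5. The planning yield in section 6.4 is 50% with an early phase response (EPR) × 50% of those with an LPR = 25%, and 25 / 0.25 = 100, which reproduces the screening number.

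**2. The boundary.** A limit of at most 20% is first breached at floor(0.20 × n) + 1 failures. At n = 100 that is 21; the count form suspends at 20.

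**3. Smaller sizes implied by rates in the documents.** Expected number challenged = 25 / LPR yield, if every LPR subject counts towards 25:

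- 50% EPR × 75% LPR (section 6.4): 25 / 0.375 = 66.7, so 67
- about 50% of those challenged (sections 1.3 and 9.3): 25 / 0.50 = 50
- 70% EPR × 75% LPR (section 6.4): 25 / 0.525 = 47.6, so 48
- 56% in a cited cat-allergen study (section 1.4): 25 / 0.56 = 44.6, so 45

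Sections 3.2 and 6.4 also speak of LPR subjects eligible for the anakinra trials, and section 4.8 makes subjects who fail essentially the same safety criteria ineligible. If only eligible LPR subjects count, and an assumed 30% fail independently of LPR, the range becomes 25 / (0.56 × 0.70) = 63.8, so 64, to 25 / (0.375 × 0.70) = 95.2, so 96.

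**4. Failures needed under each form.**

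| n | Percentage form breached at | Count form | Count as share of n |
|---|---|---|---|
| 20 | 5 | 20 | 100% |
| 45 | 10 | 20 | 44% |
| 50 | 11 | 20 | 40% |
| 64 | 13 | 20 | 31% |
| 67 | 14 | 20 | 30% |
| 96 | 20 | 20 | 21% |
| 100 | 21 | 20 | 20% |

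**5. Chance of triggering, assessed once at study end.** With X ~ Binomial(n, p), this is P(X ≥ 20) for the count and P(X ≥ floor(0.20n) + 1) for the percentage. The documents give no failure rate, so p is an assumption, shown over a range.

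| Assumed p | n = 67: count / percentage | n = 100: count / percentage |
|---|---|---|
| 20% | 0.04 / 0.48 | 0.54 / 0.44 |
| 25% | 0.22 / 0.82 | 0.90 / 0.85 |
| 30% | 0.56 / 0.96 | 0.99 / 0.98 |

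At p = 30% on the eligible-only reading, the chances are 0.46 (count) and 0.97 (percentage) at n = 64. At n = 96 both forms need 20 failures, and both give 0.98.

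**The case against.** The strongest reply is that section 9.5 contains one rule, 20%, followed by a worked conversion for the anticipated 100 subjects. A check after 20 subjects makes sense only for a proportion, so the count was never meant to apply there. This is a plausible reading, and it may be what was intended. It is not stated, however: the sentence that orders suspension uses the count, and the sentence on looks does not say which quantity is assessed.

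Second, failures cannot build up unnoticed. Each one goes to the FDA, IRB and DSMB for discussion before the next challenge, and any serious adverse event suspends the study. This stands and lowers the severity. It does not say when the cumulative number requires suspension and CBER consultation.

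Third, a reader might infer that the study is expected to end at 45 to 67 subjects, so that the count would rarely operate. The documents do not support that. They anticipate 100 and plan on a deliberately conservative yield. The 56% behind the figure of 45 comes from a study in which every participant had an EPR, whereas section 6.4 plans on half. A high failure rate also lengthens screening if ineligible subjects do not count, to about 64 to 96 under the 30% assumption. At the upper end of that range the two forms agree. At the lower end a clear gap remains.

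**Conclusion.** The inconsistency is real and its severity is moderate. Two parts rest on the text alone: the one-subject conflict at 20 of 100, and a count fixed to a sample size that section 6.4 treats as a maximum. At the look after 20 subjects the forms call for 5 and 20 failures, and the text does not choose between them.

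The size of the divergence at study end depends on how many are challenged and on the true failure rate, neither of which the documents fix. At the anticipated 100 the forms nearly coincide, and the count is slightly the more likely to trigger. At 67 the count is much less likely to trigger across assumed failure rates of 20% to 30%. These probabilities assume independent subjects, a common failure rate and a single assessment at the end. The sizes below 100 are expected values inferred from cited LPR rates, and the actual stopping number will vary.

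Nothing here shows that subjects would go unprotected, or which form of the rule is right.

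**What to change.** The sponsor and DSMB should reconcile the two sentences in section 9.5 into one rule that states:

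- the denominator that applies at each planned look: after 20 subjects, annually, and if screening stops before 100;
- whether reaching the limit exactly triggers suspension, or only exceeding it.

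Which form and which level to adopt is for them to decide.

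The cost is two sentences and no new looks. Depending on the form chosen, the reconciled rule may suspend the study earlier than a count of 20 would.
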